7.1.11. Days Alive and Out of Hospital (DAOH)

Days Alive and Out of Hospital (DAOH) calculated by subtracting days in hospital from total exposure time, where a subject's exposure is the time to death, early study discontinuation or 6 or 12 months, respectively, whichever is the smallest will be presented by means of descriptive statistics at 6 and 12 months post-implant visit.

Analysis will be done based on mITT population, PP population, and Cohort #1 population. Prior to the date of cut-off for the main analysis, it will be confirmed, if analysis based on PP population will be required.

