6.1 Study Flow

The study will implant up to 535 subjects. Assuming a dropout rate of approximately 10% by 6 months, this study will implant a maximum of 450 patients in Cohort #2 and Cohort #3. This is to achieve at least 406 implanted patients with complete follow-up at 6 months. After completion of enrollment and as soon all 406 subjects reach their 6 month follow- up visit, the 6 month primary endpoint data will be used for Premarket Approval (PMA) submission. Up to 85 subjects (cross- over from former **Control Arm**) will continued to be followed in Cohort #1.

[figure not shown]

Figure 9: Study Flow

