5.2. Key Definitions

Age

Age at screening is derived in the database and this value will be used for all analyses.

Definition of Baseline for safety assessments

Baseline will be defined as the last available value prior to the implant of Cordella PA Sensor and may be at any visit between Screening (V1) and Cordella PA Sensor Implant Visit (V2).

Definition of Baseline for PAP measurements

Baseline will be defined as value at Implant Visit (V2) obtained before discharge .

Change from Baseline

Absolute change from baseline:

Absolute change = Post-baseline value –baseline value

Time to Onset of AE

Time to onset of AE [days] = Date of start of AE – Date of implant of Cordella PA Sensor + 1

Start Day of concomitant medication

If medication starts before date of implant of Cordella PA Sensor:

Start Day of Medication = Date of start of medication – Date of implant of Cordella PA Sensor

If medication starts at/after date of implant of Cordella PA Sensor

Start Day of Medication = Date of start of medication – Date of implant of Cordella PA Sensor + 1

Incomplete start dates of medication will not be imputed. Start day of medication will be missing.

Stop Day of concomitant medication

If medication stopped before date of implant of Cordella PA Sensor:

Stop Day of Medication = Date of end of medication – Date of implant of Cordella PA Sensor

If medication stops at/after date of implant of Cordella PA Sensor

This document is confidential.

Stop Day of Medication = Date of end of medication – Date of implant of Cordella PA Sensor + 1
Incomplete end dates of medication will not be imputed. Stop day of medication will be missing.

Definition of study completed/discontinued/ongoing

A subject will be defined as study ‘completed’/‘discontinued’ based on the eCRF information. At the time of the pre-defined main analysis, subjects which are ongoing at date of cut-off will be counted as ‘ongoing’.

Time since first diagnosis of heart failure

Time since diagnosis [months] = ((Date of Screening – Date of first HF diagnosis)+1)/30

Exposure time:

which would be exact 6 or 12 months (180 or 365 days respective) post-implant visit for subjects who are still in the study at/after this timepoint.

which would be [date of last available date – date of Implant visit + 1] for subjects who withdraw from study prior to month 6 or 12 (180 or 365 days respective) post-implant visit.

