5.3. Missing Data

It is anticipated that there will be little or no missing data that would impact the ability to assess the primary endpoint. The primary efficacy analysis will be based on the mITT population and the primary safety analyses will be based on the population of subjects who underwent a device implant. The primary analysis methods naturally handle missing data by censoring subjects who have dropped out. For the primary safety analyses, the endpoints can be considered as dichotomous and the extreme cases as well as a tipping point analysis can be presented.

For all other analysis, missing data will not be replaced.

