7.1.10. Cardiac and all-cause mortality

Time to all-cause mortality in days will be defined as the time from date of Implant visit to the date of the death. In case of no death during the observation period, subject will be censored on the last available date known alive.

Similarly, time to cardiac mortality in days will be defined as the time from date of Implant visit to the date of the cardiac death. In case of no cardiac death during the observation period, subject will be censored on the last available date known without cardiac death event.

Definition of time to death (days):

In case of event, time to death = [(Date of death – date of Implant visit) + 1]

In case of no event, time to death = [(Last available date – date of Implant visit) + 1], this data will be censored.

Definition of time to cardiac death (days):

This document is confidential.

In case of event, time to cardiac death = [(Date of cardiac death – date of Implant visit) + 1]

In case of no event, time to cardiac death = [(Last available date without cardiac death event – date of Implant visit) + 1], this data will be censored.

Time to death/cardiac death will be listed and summarized by descriptive statistics.

Median duration of time to death and respective 95% CIs will be reported using Kaplan Meier estimator and Kaplan Meier plot.

```
proc lifetest data = xxx  
    time days * censor(1);  
run;
```

Analysis will be done based on mITT population, PP population, and Cohort #1 population. Prior to the date of cut-off for the main analysis, it will be confirmed, if analysis based on PP population will be required.

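### Days alive and out of hospital counts unobserved time after a live withdrawal as lost days, exactly as it counts time after death

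*SAP*

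**What the plan says.** DAOH is secondary efficacy endpoint 8 in SAP 3.3. SAP 7.1.11 gives the only formula: it is "calculated by subtracting days in hospital from total exposure time". The same sentence then fixes when the clock stops, with one rule for every kind of ending: "where a subject's exposure is the time to death, early study discontinuation or 6 or 12 months, respectively, whichever is the smallest". Protocol 5.1 and 10.4 name the endpoint without a calculation.

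SAP 5.2 defines exposure in the same way. The full horizon is one "which would be exact 6 or 12 months (180 or 365 days respective) post-implant visit". A separate rule "for subjects who withdraw from study prior to month 6 or 12" stops exposure at the last available date.

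The day count "will be presented by means of descriptive statistics at 6 and 12 months post-implant visit"; under SAP 5.1 that means n, mean, SD, median, minimum and maximum. The SAP's index of tables repeats it by sex, by ejection fraction, for the per-protocol set and for Cohort #1.

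On missing data, SAP 5.3 speaks of censoring only for the primary analyses and then says: "For all other analysis, missing data will not be replaced". By contrast, SAP 7.1.10, the section just before, separates death from departure: without a death, the "subject will be censored on the last available date known alive".

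The only planning figure for losses is in Protocol 6.1: "Assuming a dropout rate of approximately 10% by 6 months".

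**The concern.** DAOH is meant to charge a subject for days dead and days in hospital. Under SAP 7.1.11 it also charges for days on which nobody was looking. A subject who leaves alive on day 30 scores the same as one who dies on day 30.

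The exposure rule itself is sound in SAP 7.1.1, where it is the offset of the Poisson model and so acts as a denominator. In 7.1.11 the same quantity becomes the outcome, and truncation by withdrawal then reads as a bad result.

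Two things are at stake. Mean DAOH is too low by an amount that depends on retention. And because the table is repeated by sex, by ejection fraction and for Cohort #1, groups that differ only in retention can show a DAOH difference unrelated to death or hospital stay. A comparison with another study's DAOH would be affected in the same way.

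**Working it through.** **1. The plan's own figure.** The documents give no expected DAOH. The nearest stated figure is 406 evaluable subjects from 450 implanted at about 10% dropout (Protocol 6.1 and 10.3): 450 × (1 − 0.10) = 405, which agrees with 406 to rounding.

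**2. The rule for one subject.** DAOH = min(day of death, day of discontinuation, T) − hospital days, with T = 180 or 365.

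- Death on day 60 with 5 hospital days: 60 − 5 = 55.
- Live withdrawal on day 60 with 5 hospital days: 60 − 5 = 55.

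The result is the same at both horizons.

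**3. Size in the mean at 6 months.** Assume that withdrawals and deaths are spread evenly over 180 days, so that each costs 90 days on average. Days removed from the mean = proportion × 90.

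| Component | Proportion | Days removed |
|---|---|---|
| Live withdrawal, all of the 10% | 10% | 0.10 × 90 = 9.0 |
| Live withdrawal, half of it | 5% | 0.05 × 90 = 4.5 |
| Live withdrawal, if the 10% includes deaths at about 6% | 4% | 0.04 × 90 = 3.6 |
| Deaths, CHAMPION row of Protocol 10.3 | 15/270 = 5.6% | 0.056 × 90 = 5.0 |
| Deaths, MEMS PAS row of Protocol 10.3 | 107/1200 = 8.9% | 0.089 × 90 = 8.0 |

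The 6% is an assumed round value near the lower of the two mortality figures. If the 10% included deaths at 8.9%, only 1.1% would be live withdrawals, or about 1.0 day.

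**4. Share of the shortfall from withdrawal plus death.**

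- 10% withdrawal: 9.0/(9.0 + 5.0) = 64%, or 9.0/(9.0 + 8.0) = 53%.
- 4% withdrawal with 6% deaths (0.06 × 90 = 5.4 days): 3.6/(3.6 + 5.4) = 40%.

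**5. Hospital days.** These can only be sketched. The assumed rate of 0.34 events less about 0.06 deaths leaves 0.28 heart-failure admissions per subject. At an assumed 5 to 7 days each, that is 0.28 × 5 = 1.4 to 0.28 × 7 = 2.0 days. SAP 7.1.11 does not limit hospital days to heart failure, and the documents give no all-cause admission rate, so the true figure is unknown and probably higher.

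**6. The median.** With 10% withdrawn and 5.6% to 8.9% dead, 15.6% to 18.9% of subjects are truncated. The median subject still has full follow-up, so the median moves little.

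**The case against.** The strongest reply is that little depends on this. DAOH is one of 15 secondary efficacy endpoints, with no hypothesis, performance goal or place in the gatekeeping sequence. The error lowers the result and so works against the device. Withdrawals with reasons, Kaplan-Meier mortality and heart-failure hospitalizations are all tabulated separately, so a careful reader could see how much retention contributes. All of this stands and limits the weight of the point. It does not correct the DAOH table.

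A reader might go further and infer that withdrawal is the largest source of lost days, so that DAOH mainly measures retention. The documents do not support that.

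- The 10% is applied to reach subjects with complete 6-month follow-up, and SAP 7.1 recognises death as a recorded reason for discontinuation. The 10% may therefore include deaths. With 6% deaths inside it, withdrawal costs 3.6 days against 5.4.
- At 5% withdrawal the cost is 4.5 days, below the 5.0 for the lower mortality.
- At 8.9% mortality, deaths plus the sketched hospital days come to 8.0 + 1.4 = 9.4 up to 8.0 + 2.0 = 10.0 days, more than the 9.0 for a full 10% withdrawal.

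A fair objection also applies to the remedy. As a simple percentage, a subject who leaves well on day 5 scores 5/5 = 100%, level with a completer who was never admitted. If sicker subjects leave, that would favour the device.

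**Conclusion.** The definition is wrong as written for a named secondary endpoint: after a live withdrawal, unobserved days are scored as days not alive and out of hospital, and nothing elsewhere in the protocol or SAP repairs this. The equality of death and withdrawal follows from the formula and needs no assumption.

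The size does need assumptions: losses at mid-window on average, mortality borrowed from the source table in Protocol 10.3, and an unknown split of the planned 10% between deaths and withdrawals. On those terms, live withdrawal of 4% to 10% lowers the 6-month mean by about 3.6 to 9.0 days, against about 5.0 to 8.0 for deaths. That is material, but withdrawal is not necessarily the largest part. The primary efficacy conclusion and its type I error are unaffected. The change should be made, but the trial's main result does not depend on it.

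**What to change.** In SAP 7.1.11, report DAOH as a percentage of potential follow-up. Use 180 (or 365) days as the denominator for completers and for subjects who died, and days to withdrawal for subjects who left alive. Summarise it with person-time weighting, as total DAOH divided by total potential days, so that a very short follow-up contributes only its own days. In the day-60 example, the death then contributes 55 of 180 days (30.6%) and the withdrawal 55 of 60 (91.7%).

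Keep the present raw-day summary as a conservative sensitivity analysis, labelled as giving no credit after withdrawal. State the assumption beside the main table: the percentage treats time after withdrawal as resembling observed time, which is optimistic if sicker subjects withdraw. The two summaries together show how far this matters.

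The same edit should say how 12-month DAOH handles subjects still in the study with fewer than 365 days when the main analysis is run after Month 6. SAP 5.2 gives no exposure rule for them, and their count could be shortened in the same way.

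The cost is one extra denominator built from dates already collected, plus the stated assumption.

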7.1.12. Hospital Outpatient IV diuretic visits

This endpoint will be analyzed similarly as the primary endpoint in Section [7.1.1](#).

Analysis will be done based on mITT population, PP population, and Cohort #1 population. Prior to the date of cut-off for the main analysis, it will be confirmed, if analysis based on PP population will be required.

7.1.13. Heart failure related medication changes

Heart failure related medication change since last visit is collected via eCRF 'Has there been a change in the cardiovascular medication since last visit' and will be summarized by visit presenting the number and percentage of subjects with and without any change in HF medication.

Analysis will be done based on mITT population, PP population, and Cohort #1 population. Prior to the date of cut-off for the main analysis, it will be confirmed, if analysis based on PP population will be required.

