Regular review of the patient’s data will allow proactive heart failure management. It is assumed that post sensor implant, more intense HF management is needed to optimize the patient’s HF treatment for a period of 1-3 months, as the patient is treated to target pressures per the guidelines in Appendix 14.5 and GDMT. Data displayed at the myCordella™ PMP will enable clinicians to effectively adjust medication dosages (e.g., drug titration) during this “optimization” period. In the following “stabilization” phase, the clinician will be able to quickly assess the patient daily health status via the myCordella™ PMP and take action as needed. As it is the nature of this particular disease, even under optimal treatment, HF patients are likely to worsen again over time. Regular review of the patient PAP trends, in addition to other data provided by the Cordella System, will allow the clinician to proactively treat the patient before full decompensation and hospitalization.

When worsening occurs, the patient will undergo again the “optimization” phase, followed by the “stabilization” phase as per the guidelines in Appendix 14.5.

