8.1.22 Concomitant Medications

Administration of beta blockers (BB), ACE-I, ARB, ARNI, mineralocorticoid receptor antagonists, (MRA), nitrates, hydralazine, inotropes, anticoagulants, anti-arrhythmics, antiplatelet medications, antibiotics, diuretics and antihypertensive medications, and any other cardiac medications at all study visits between screening and year 5 will be recorded.

Information collected at time of visit will include:

- Drug
- Dose
- Route of administration

Adverse Events

Any Concomitant Medications taken prior, up to onset and to treat an Adverse Event will be collected at the time of each event.

Anticoagulation

For subjects who are not being treated with chronic anticoagulant therapy, it is recommended to use dual antiplatelet therapy with aspirin and clopidogrel, (or prasugrel, ticagrelor) for 30 days post implant.

Subjects who are currently on anticoagulant therapy, or those in which chronic anticoagulant therapy is indicated for HF treatment should discontinue use of anticoagulant therapy 1-2 days prior to the Cordella Sensor implant and restart treatment post- implant. An INR of <1.5 is recommended prior to sensor implant for subjects who were previously on anticoagulant therapy. The standard of care as bridge therapy to Cordella Sensor placement should be used in patients who were on anticoagulant therapy.

Post 30 days, continuous single antiplatelet therapy with aspirin indefinitely is recommended.

It is important to resume or initiate antiplatelet or anticoagulant therapy post-implant to reduce the likelihood of thrombotic events.

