12 DOCUMENTATION OF TRIAL DATA

12.1 Case Report Forms

An Electronic Data Capture (EDC) system will be utilized to collect all subject data during the course of the study. Data must be entered into eCRFs in English. The eCRFs are to be completed within 72 hours of the subject's visit, with the exception of results from tests performed outside the investigator's office, so that they always reflect the latest observations on the subjects participating in the study. This includes all medication changes in between study visits. A predetermined/designated individual(s) will be responsible for completion of the Electronic Case Report Forms (eCRFs). The PI will ultimately be responsible for the review, completion and accuracy of data entered into the eCRF.

Completed eCRFs will be verified by a Sponsor monitor at the site at regular intervals throughout the study. The Investigator will allow the monitor and the regulatory bodies (Competent Authorities (CAs)) to review the study files, subject eCRFs, medical records and other study-related documents.

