3.3. Secondary Efficacy Endpoints

1. Incidence of HF Hospitalizations or all-cause mortality at 12 months
2. Number of HF Hospitalizations at 6 and 12 months post-implant compared to the number of HF Hospitalizations in the 6 and 12 months prior to implant
3. Comparison of the number of HF Hospitalizations or Emergency Department/ Hospital Outpatient IV diuretic visits of Cohort #1 and Cohort #2 + #3 at 6 and 12 months post implant
4. Change of N-terminal pro B-type Natriuretic Peptide (NT-proBNP) from Baseline through 6 and 12 months
5. Combined outcome of:
 - a. First and recurrent HF Hospitalizations
 - b. Heart failure Emergency Department/ Hospital Outpatient IV diuretic visits
 - c. all-cause mortalityat 6 months, added together with equal weighting into a total number of events.
6. Heart failure hospitalization or HF Emergency Department/ Hospital Outpatient IV diuretic visits at 6 and 12 month
7. Cardiac and all-cause mortality
8. Days Alive and Out of Hospital (DAOH)
9. Intravenous (IV) diuretic visits
10. Heart failure related Medication changes
11. Change in PAP:
 - a. From Baseline through 6 and 12 months in subjects with a baseline mPAP
 - i. above target range
 - ii. within or below target range
 - iii. Overall
 - b. Before and after 6-Minute Walk Test
12. Percentage of device success as documented by ability of the System to successfully transmit PAP data
13. Subject Outcome Measures, measured by Kansas City Cardiomyopathy Questionnaire (KCCQ)
14. Functional status improvement, as measured by NYHA and 6-Minute Walk Test
15. Health Economic Analysis (will be covered separately)

This document is confidential.

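### The endpoint for heart failure related medication changes is read from a yes/no item on any cardiovascular drug, so it cannot isolate HF titration, and its percentages are not comparable across unequal visit gaps

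*SAP*

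**What the plan says.** SAP 3.3 lists the endpoint as "Heart failure related Medication changes". SAP 7.1.13 takes it from the eCRF question "Has there been a change in the cardiovascular medication since last visit" and reports, by visit, the "number and percentage of subjects with and without any change in HF medication". Nothing in 7.1.13 limits the drug class, excludes antithrombotics, counts changes, records their direction or allows for the length of the interval. Tables 14.2.2.10.1 to 14.2.2.10.5 are the only tables planned for the endpoint.

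Protocol 8.1.22 lists the drugs to be recorded at each visit. The list includes "anticoagulants, anti-arrhythmics, antiplatelet medications, antibiotics, diuretics and antihypertensive medications, and any other cardiac medications". For subjects not on chronic anticoagulation, "it is recommended to use dual antiplatelet therapy with aspirin and clopidogrel, (or prasugrel, ticagrelor) for 30 days post implant". It continues: "Post 30 days, continuous single antiplatelet therapy with aspirin indefinitely is recommended". Subjects on anticoagulants are to pause before implant and resume afterwards.

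Protocol 8.1.20 expects that after implant "more intense HF management is needed to optimize the patient", for a period of 1 to 3 months, followed by a stabilization phase. Protocol 12.1 says of eCRF entry: "This includes all medication changes in between study visits".

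**The concern.** The sensor has no direct therapeutic effect (Protocol 1.3). Any benefit has to come through what clinicians do with the pressures, chiefly through drug treatment, so this endpoint is the one that should show the mechanism at work. It has two weaknesses.

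- **Scope.** The question asks about cardiovascular drugs and the table is labelled HF drugs. The Protocol recommends non-HF cardiovascular drug changes in the same weeks in which it expects most HF titration. A reader of the table cannot tell one from the other.
- **Interval.** A yes/no answer since the last visit is more likely to be yes when the last visit was longer ago. A percentage by visit therefore mixes the rate of change with visit spacing, and a subject with one change counts the same as a subject with ten.

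The trial is single-arm, so no concurrent control shares the artefact and cancels it.

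**Working it through.** The documents give no expected percentage, change rate or power for this endpoint, so there is no figure of the plan's to reproduce. The rates and shares below are assumptions used for illustration.

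**1. Look-back intervals.** Visits fall at implant and then at Months 1, 3, 6, 12, 18 and 24 and Years 3, 4 and 5 (Protocol synopsis). The gaps are 1, 2, 3, 6, 6, 6, 12, 12 and 12 months. SAP 1.2 limits by-visit summaries in the main analysis to data up to V5, so that analysis uses gaps of 1, 2 and 3 months only. The 6- and 12-month gaps enter at the follow-up analysis.

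**2. Effect of the gap alone.** With a constant rate of h changes per month, P(yes) = 1 − exp(−h × gap).

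| Assumed h per month | V3 (1 month) | V4 (2 months) | V5 (3 months) | 6-month gap | 12-month gap |
|---|---|---|---|---|---|
| 0.05 | 5% | 10% | 14% | 26% | 45% |
| 0.2 | 18% | 33% | 45% | 70% | 91% |
| 0.4 | 33% | 55% | 70% | 91% | 99% |

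At any constant rate the percentage rises with the gap. Its level depends on the rate. Reaching 90% yes needs h = −ln(0.1)/gap: 2.303/6 = 0.38 per month at a 6-month gap and 2.303/12 = 0.19 at a 12-month gap.

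**3. Falling rate.** A constant rate is not what Protocol 8.1.20 expects. Suppose the rate is 0.5 per month in month 1 and 0.2 per month in months 3 to 6, a fall of (0.5 − 0.2)/0.5 = 60%. V3 shows 1 − exp(−0.5 × 1) = 39% and V5 shows 1 − exp(−0.2 × 3) = 45%. The table goes up while the rate goes down.

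**4. Antithrombotic changes at V3.** Let a be the share of subjects with an antithrombotic change in the look-back, q the chance that the site counts it, and f the chance of a true HF drug change in month 1. Then P(yes) = 1 − (1 − a × q)(1 − f).

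| a | q | f = 0 | f = 0.5 |
|---|---|---|---|
| 0.5 | 0.5 | 25% | 62% |
| 0.9 | 0.5 | 45% | 72% |
| 0.9 | 1 | 90% | 95% |
| 1 | 1 | 100% | 100% |

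The documents fix none of a, q or f. The illustrative inputs span 25% to 100%, so the inflation is possible but cannot be sized.

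**5. Where the day-30 step falls.** V3 has a window of ±7 days (SAP 5.4), roughly days 23 to 37. The step to a single antiplatelet agent therefore lands in the look-back of V3 for some subjects and V4 for others.

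**The case against.** A reader might infer that nearly every subject will be a yes at Months 1 to 3 because of antithrombotics, and that the long gaps will make nearly everyone a yes later. The documents do not support either inference.

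- The antiplatelet regimens are recommended, and some subjects may already be taking them.
- Medications are also recorded at the implant visit, so the anticoagulant pause, or the start of dual therapy, may be captured there and not count as a change since the last visit at V3. A pause with resumption may be answered no.
- The eCRF and its completion instructions are not in the documents, so how sites read the question is unknown.
- Early yes answers will include genuine HF titration, which Protocol 8.1.20 expects in that period.
- Saturation at later visits needs roughly 0.2 to 0.4 changes per subject-month, an assumed figure, and those gaps are outside the main analysis.

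All of this stands, and it rules out any claim about the size of the inflation. It does not touch the mismatch between item and label, or the dependence on gap length, which is already present over the 1-, 2- and 3-month intervals of the main analysis.

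It can also be said that other outputs cover the ground: ATC summaries (SAP 6.5), concomitant medication by category (Table 14.1.4.13) and a listing of HF medication changes (Listing 16.2.6.5). The summaries show which drugs were taken, not what changed or when, and a listing is not a summary of the endpoint.

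**Conclusion.** The point holds in a limited form. The item used for endpoint 10 cannot separate HF from other cardiovascular drug changes. It is open to inflation at V3 and V4 by changes the Protocol recommends, by an amount the documents do not allow one to estimate. The percentages are also not comparable between visits: under a constant rate they rise with the gap, for example 18%, 33% and 45% at V3 to V5 at an assumed 0.2 changes per month, and under a falling rate they can move in the wrong direction. The mismatch of scope follows from the wording alone; the size of the interval effect rests on the assumed rates.

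The importance is moderate. The endpoint is descriptive and lies outside the gatekeeping in SAP 2.4.2, so no primary efficacy or safety conclusion depends on it. What would suffer is any statement about how far, and when, HF therapy was adjusted after implant.

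**What to change.** Rewrite SAP 7.1.13 so that the endpoint is derived from the medication records instead of the yes/no item.

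- Prespecify the HF drug classes, for example beta blocker, ACE-I/ARB/ARNI, MRA, SGLT2 inhibitor, diuretic and nitrate/hydralazine, and exclude antiplatelets, anticoagulants and other non-HF classes.
- Report the number of changes divided by subject-months of follow-up for 0–1, 1–3, 3–6 and 6–12 months after implant, overall and by class.
- Report direction (start, increase, decrease, stop) where the dose records allow it.
- State how partial dates are assigned to an interval, since SAP 5.2 leaves incomplete start and stop dates unimputed.
- Keep the yes/no item as a listing, or retitle its tables as any cardiovascular medication change.

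Drug, dose and route are recorded (Protocol 8.1.22), start and stop days are derived (SAP 5.2), and changes between visits are entered in the eCRF (Protocol 12.1). The cost is SAP text, class coding and programming, with no new assessments. The change implies no view on antithrombotic management.
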